#### **REDUCED FOLLOW-UP SCHEDULE**

Complete the following assessments at the intervals (+/- 7 days) indicated below relative to the day the subject discontinued study treatment. Continue conducting these assessments at the defined intervals until the subject reaches two years post **last** transplant.

- Assess SAEs and hypoglycemic events: q1 month. If subject does not come to the study site for the visit, attempt to obtain information via a phone contact.
- Alloantibody (central lab): q 1 month for the first 3 months and q 3 months thereafter.
- Immunogenicity Samples: for subjects who discontinue belatacept, collect samples at 4 weeks and 8 weeks post last dose

Complete the following assessments at 1 and 2 years (+/- 14 days) post **initial** transplant:

- Assess SAEs and hypoglycemic events
- Alloantibody (central lab)
- HbA1c (central lab)
- 90 minute c-peptide post MMTT (central lab)
- Serum creatinine (central lab)
- QOL questionnaire (via mail or in-person)

Complete the following assessments at 1 and 2 years (+/- 7 days) post **last** transplant:

- Assess SAEs and hypoglycemic events
- QOL questionnaire (via mail or in-person)

*Appendix 6: Study Contacts*

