#### 4.1.2.2 SECONDARY SAFETY ENDPOINTS

- Safety, including incidence of post-transplant infections, malignancies, morbidity, and other AEs (e.g., increased body weight and hypertension) associated with conventional immunosuppression.
- Renal function as measured by serum creatinine, GFR and other relevant laboratory parameters.
- Lipid profiles (triglycerides, total cholesterol, LDL cholesterol, HDL cholesterol) over time.

At  $75 \pm 5$  days following each transplant, at  $365 \pm 14$  days following the first and final islet transplant, and at two years following the final islet transplant:

- The incidence and severity of AEs related to the islet transplant procedure including: bleeding (> 2 g/dL decrease in hemoglobin concentration); segmental portal vein thrombosis; biliary puncture; wound complication (infection or subsequent hernia); and increased transaminase levels (> 5 times upper limit of normal [ULN])
- The incidence and severity of AEs related to the immunosuppression including: allergy; reduction in GFR; addition or intensification of anti-hypertensive therapy;

- gastrointestinal toxicity; neutropenia, anemia, or thrombocytopenia; viral, bacterial, or fungal infections; and benign or malignant neoplasms
- The incidence of a change in the immunosuppression drug regimen
  - The incidence of immune sensitization defined by presence of anti-HLA antibodies absent prior to transplantation
  - The incidence of discontinuation of immunosuppression

At  $365 \pm 14$  days following the first islet transplant:

- The incidence of worsening retinopathy as assessed by change in retinal photography from pre-transplant. If pupil dilation is not possible, then a manual ophthalmologic evaluation can be substituted.

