#### 5.7.2 Premature Discontinuation of Study Treatment (Transition to “Off-Protocol” Treatment)

Study treatment may be prematurely discontinued for any subject for any of the following reasons:

1. The subject is unwilling or unable to comply with the protocol.
2. The investigator believes that the study treatment is no longer in the best interest of the subject.
3. Graft Failure (see Study Definitions).
4. Any clinical AE, laboratory abnormality, or intercurrent illness which, in the opinion of the investigator, indicates that continued treatment with study therapy is not in the best interest of the subject. The agent(s) to which the event is attributed will be discontinued.
5. The subject becomes pregnant
6. Missing 2 consecutive belatacept infusions
7. The development of belatacept is terminated by the manufacturer (BMS)
8. The subject is imprisoned or compulsorily detained for the treatment of either a psychiatric or physical illness (e.g., infectious disease).

Subjects who prematurely discontinue study treatment will remain in the study until normal termination, for the purpose of monitoring safety and efficacy parameters and will enter the reduced follow-up scheduled outlined in Appendix 5. Data from these subjects will be used in the intent-to-treat analysis. These subjects are permitted to simultaneously enroll in a CIT or site-specific graft failure follow-up protocol, if available.

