## 8.2 Adverse Events

### 8.2.1 Collecting Procedure

AEs that are associated with a protocol mandated procedure, which is not part of the normal standard of care of the participant, and **severe hypoglycemic events** (see study definitions) will be collected beginning immediately after the enrollment consent has been obtained. All other AEs will be collected beginning immediately after randomization. All AEs will continue to be collected until study completion, or for 56 days after the subject prematurely withdraws from the study. AEs will be followed until the time the event is resolved, stabilized, or the subject completes or withdraws from the study, whichever comes first. For transplants that occur as a standard of care procedure at the University of Alberta, adverse events will be collected and submitted by the site investigator until all CIT04 study visits have been completed. If a subject enrolls in a non-CIT islet transplant study, adverse events will no longer be collected in CIT starting at the time of the non-CIT study intervention. All adverse event reporting from that point on will be done through the non-CIT study.

AEs may be discovered through any of these methods:

- Observing the subject.
- Questioning the subject, which should be done in an objective manner.
- Receiving an unsolicited complaint from the subject.
- An abnormal value or result from a clinical or laboratory evaluation (e.g., a radiograph, an ultrasound, or an electrocardiogram) can also indicate an AE. If this is the case, then the evaluation that produced the value or result should be repeated

until the value or result returns to normal or can be explained and the subject's safety is not at risk. If an abnormal value or result is determined by the investigator to be clinically significant, it must be indicated as such on the appropriate laboratory evaluation form(s), and must also be reported as an adverse event on the adverse event form AE.

AEs should be followed to resolution or stabilization, and reported as SAEs if they become serious. This also applies to subjects experiencing AEs that cause interruption or discontinuation of investigational product, or those experiencing AEs that are present at the end of their participation in the study; such subjects should receive post-treatment follow-up as appropriate. If an ongoing AE changes in its severity or in its perceived relationship to study drug, a new AE entry for the event should be completed.

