### **8.2.2 Recording Procedure**

Throughout the study, the investigator will record all adverse events on the appropriate AE case report form (CRF) regardless of their severity or relation to study medication or study procedure. The investigator will treat subjects experiencing AEs appropriately and observe them at suitable intervals until their symptoms resolve or their status stabilizes.

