**Appendix 2: Continuation of Appendix 1 Schedule of Events (Subjects with Subsequent CIT Transplants)**

Subjects who receive a subsequent islet transplant should continue their study visits according to this Schedule of Events until one year (365 +/- 5 days) after the final islet transplant. Additional visits - outlined in Appendix 3 - will also need to be completed after each subsequent transplant. After day 365 post final transplant, subjects should stop following this schedule, and complete the follow-up visits outlined in Appendix 4: *Schedule of Events for 1-Year Additional Follow-Up*.

Time points (in days relative to 1 st transplant)	392	420	448	476	504	532	560	588	616
Visit Number	22	23	24	25	26	27	28	29	30
Visit Windows (in days)	±5	±5	±5	±5	±5	±5	±5	±5	±5
Equivalent Week	W56	W60	W64	W68	W72	W76	W80	W84	W88
GENERAL ASSESSMENTS									
Physical Exam			X			X			X
QOL			X			X			X
AE/Hypo Event/Toxicity Assessment	X	X	X	X	X	X	X	X	X
LOCAL LABORATORY ASSESSMENTS									
CBC (WBC + Diff & Plat)			X			X			X
Chemistry 			X			X			X
Lipids			X			X			X
Pregnancy test (WOCBP) 	X	X	X	X	X	X	X	X	X
CENTRAL LABORATORY ASSESSMENT									
HbA1c			X			X			X
Fasting serum glucose & c-peptide & serum creat 	X	X	X	X	X	X	X	X	X
90 min  c-peptide/glucose (MMTT) 			X			X			X
Atherogenic Profile 	1 year post-final transplant								
LOCAL METABOLIC ASSESSMENTS									
BSR eCRFs 			X			X			X
CALCULATED METABOLIC ASSESSMENTS									
MAGE			X			X			X
LI			X			X			X
Clarke Score						X			
HYPO			X			X			X

Time points (in days relative to 1 st transplant)	392	420	448	476	504	532	560	588	616
Visit Number	22	23	24	25	26	27	28	29	30
Visit Windows (in days)	±5	±5	±5	±5	±5	±5	±5	±5	±5
Equivalent Week	W56	W60	W64	W68	W72	W76	W80	W84	W88
CALCULATED METABOLIC ASSESSMENTS (continued)									
Beta Score			X			X			X
C-peptide (glucose X creatinine) ratio	X	X	X	X	X	X	X	X	X
IMMUNOSUPPRESSION LEVELS									
Belatacept trough levels 	X	X	X	X	X	X	X	X	X
MECHANISTIC ASSAYS									
Alloantibodies 			X			X			X
Autoantibodies 			X			X			X
Immunogenicity samples 						X			
ARCHIVED SAMPLES									
Serum			X			X			X
Plasma			X			X			X

 EBV by PCR should only be done post-randomization if reactivation is suspected.

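### After treatment stops, Appendix 5 solicits only SAEs and hypoglycemic events while Sections 8.2.1 and 8.2.2 require all AEs, so late AE incidence can be biased downward

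*Protocol*

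**What the plan says.** Four parts of the protocol bear on this.

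- **Collection.** Section 8.2.1: "All AEs will continue to be collected until study completion, or for 56 days after the subject prematurely withdraws from the study".
- **Recording.** Section 8.2.2: "Throughout the study, the investigator will record all adverse events on the appropriate AE case report form (CRF) regardless of their severity".
- **Status of subjects who stop treatment.** Section 5.7.2: "Subjects who prematurely discontinue study treatment will remain in the study until normal termination, for the purpose of monitoring safety and efficacy parameters". It sends them to the Appendix 5 schedule and adds: "Data from these subjects will be used in the intent-to-treat analysis".
- **What Appendix 5 asks for.** The monthly item is "Assess SAEs and hypoglycemic events: q1 month". The visits at 1 and 2 years after the initial transplant, and again after the last transplant, carry the same SAE and hypoglycemia item. The regular schedule has a broader one; Appendix 2, for instance, lists "AE/Hypo Event/Toxicity Assessment".

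A further rule stands under Section 8.2.2, in the part on reporting AE information following study completion. Despite that heading, its text is tied to the end of dosing. It calls for all SAEs in the 56 days after dosing stops, later SAEs thought related to the product, and a named list (death, graft loss, malignancy, PTLD, serious infection) to the end of the study.

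The endpoint affected is in Section 4.1.2.2: "The incidence and severity of AEs related to the immunosuppression including" allergy, reduced GFR, added anti-hypertensive therapy, gastrointestinal toxicity, cytopenias, infections and neoplasms. It is read at Day 75 after each transplant, at Day 365 after the first and final transplants, and at two years after the final one. It is not restricted to serious events.

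**The concern.** Subjects on Appendix 5 are still study subjects, so the general rule promises full AE data on them. The schedule that sites will follow visit by visit does not ask for those data. A site that treats Appendix 5 as complete will have no scheduled prompt for a non-serious event after the switch.

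The loss would not be at random. Section 5.7.2 lists adverse events, graft failure and inability to comply among the reasons for stopping. These subjects remain in the denominator, so any event missed among them can only lower the reported incidence. Safety is part of the primary objective (Section 2.1), and the AE profile of a calcineurin inhibitor-free regimen is a large part of what the pilot is meant to show.

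**Working it through.** The protocol states no AE rate or discontinuation rate, so there is no figure to reproduce. The check compares the texts, followed by an illustration on assumed inputs.

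**1. Does the 56-day limit in Section 8.2.1 resolve the conflict?** No. It applies to premature withdrawal from the study. Under Section 5.7.2 these subjects have stopped treatment and remain in the study, so the limit that applies to them is study completion.

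**2. Does the Section 8.2.2 text on the period after dosing resolve it?** No. It is SAE-based and closer to Appendix 5, which suggests that narrower collection may have been intended. But it sits beside the instruction to record all AEs throughout the study, and no text ranks one above the other.

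**3. Are Appendix 5 subjects all off immunosuppression?** Not necessarily.
- Section 5.7.2, item 4: only the agent or agents blamed for the event are stopped.
- Section 6.2.2: after primary non-function belatacept ends, but the other immunosuppression continues for a time and is tapered.
- Section 7.6: subjects who do not meet the criteria for a further transplant go to Appendix 5, with no statement that they have stopped immunosuppression.

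By contrast, Sections 5.7.1.2 and 7.6.1 stop immunosuppression after graft failure with no further transplant possible, or after graft failure following the second transplant.

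**4. Which laboratory tests remain?** Appendix 5 has no CBC, chemistry panel or GFR. Serum creatinine is kept at 1 and 2 years after the initial transplant. Neutropenia, anemia and thrombocytopenia therefore lose the test that would show them.

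**5. Illustration of size.** N = 10 (Section 10.4). Let k be the number of subjects on Appendix 5 and q the chance that such a subject's first listed non-serious event falls after the switch and goes unrecorded. Both k and q are assumptions.

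- Expected undercount = k × q / 10.
- Chance of missing at least one affected subject = 1 − (1 − q)^k.

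| k | Undercount, q = 0.1 to 0.5 | Chance of at least one missed |
|---|---|---|
| 1 | 1 to 5 points | 0.10 to 0.50 |
| 3 | 3 to 15 points | 0.27 to 0.88 |
| 5 | 5 to 25 points | 0.41 to 0.97 |

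For example, with k = 3 and q = 0.5: 3 × 0.5 / 10 = 15 points, and 1 − 0.5³ = 0.875. One missed subject is 1/10 = 10 points.

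Unobserved time is a different quantity. If k subjects stop at an assumed month 4 of 24, the share of person-months without full AE collection is k × 20/240: 8.3% for k = 1, 25% for k = 3, 41.7% for k = 5. These are not undercounts of incidence, because a subject who had the event before the switch is already counted.

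**The case against.** The strongest reply is that Appendix 5 only schedules assessments. It does not say that non-serious events go unrecorded. Sections 8.2.1 and 8.2.2 still apply, and 8.2.1 lists passive routes such as observation, unsolicited complaints and abnormal results. This stands: what is lost is systematic solicitation, and the undercount depends on sites treating Appendix 5 as the whole requirement.

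It can also be said that toxicity leading to discontinuation occurs before the switch, under full collection, and that events in a subject fully off immunosuppression are mostly not events of the regimen. Counting them could even charge off-drug events to it. This stands too, and limits the concern mainly to subjects who remain on some agents.

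Two further limits are fair. Section 8.2.3.2 collects attribution only for SAEs, in every subject, so added non-serious events would carry no relatedness. And an extra question, possibly by telephone, cannot detect a cytopenia.

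A reader might infer that non-serious events simply vanish after the switch, that AE rates are certainly understated by something like the 25% of person-time above, or that the listed endpoint events are mostly non-serious. The documents support none of these. Passive recording remains required, person-time does not measure subject-level incidence, and Section 4.1.2.2 gives no split by seriousness.

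**Conclusion.** The inconsistency is real: Sections 8.2.1 and 8.2.2 require all AEs to study completion, while Appendix 5 and the post-dosing text under 8.2.2 are SAE-based, for subjects whom Section 5.7.2 keeps in the study and in the analysis. If sites follow Appendix 5, the incidence of immunosuppression-related AEs at Day 365 and two years can be biased downward. The direction follows from the fixed denominator. The size cannot be computed from the protocol, and the table above is illustrative only.

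The effect falls on a descriptive secondary safety endpoint in a 10-subject single-arm pilot and leaves the primary endpoint's definition and analysis unchanged. It should still be corrected, because it is cheap to correct and the missing information cannot be fully recovered afterwards.

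**What to change.** - In Appendix 5, replace SAEs with AEs and SAEs at the monthly contact and at the 1- and 2-year visits. Align the post-dosing text under Section 8.2.2, so that it, Sections 8.2.1 and 8.2.2 and Appendix 5 state one rule.
- For any period without full AE collection, report non-serious AE incidence over the fully observed period or per person-time observed, separating on-treatment from off-treatment time.
- State that laboratory-detected events such as neutropenia and anemia are not systematically ascertained under Appendix 5, which has no CBC.

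The cost is slightly more AE questioning and data entry at contacts that already take place. No treatment rule changes. The absence of attribution for non-serious events is a separate limit that this change does not remove.

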## Protocol Synopsis

Title	Islet Transplantation in Type 1 Diabetes
Clinical Phase	Phase 3
IND Sponsor	DAIT/NIAID/NIH
IND Number	Exempt
Activation Date	June 2011
Accrual Objective	Approximately 75 subjects
Accrual Period	N/A
Follow-up Period	Varies; the CIT08 follow-up period begins after termination from the CIT parent study and ends on the final date of the CIT08 study, 01Jul2017.
Study Design	A single-arm, multi-center cohort study in islet transplantation
Treatment Description	Subjects who have received an islet transplant during participation in CIT02, CIT03, CIT04, CIT05, CIT06, or CIT07 will undergo additional follow-up, including annual assessments of graft function (if applicable) and safety.
Primary Endpoint	The primary endpoint is duration of sustained islet allograft function as determined by evidence from MMIT of C-peptide production at each anniversary of the final transplant. A C-peptide level greater than or equal to 0.3 ng/mL at 0, 60, or 90 minutes will be considered evidence of islet allograft function.
Secondary Endpoints	Secondary endpoints include the following: 

• Serum creatinine and calculated eGFR at each annual study visit

• Incidence of serious adverse events during the 12-month period preceding each annual study visit

• Insulin requirements during a one-week period preceding each annual study visit

• Incidence of severe hypoglycemic events during the 12-month period preceding each annual study visit

• HbA1c levels at each annual study visit

• All causes of mortality

Inclusion Criteria	

1. Participation in any of the following CIT parent studies: CIT02, CIT03, CIT04, CIT05, CIT06, and CIT07.

2. Willingness of participants to continue to use an approved method of contraception during and 4 months after study participation.

3. Ability to provide written informed consent.

Exclusion Criteria	

1. For female subjects: Positive pregnancy test, presently breast-feeding, or unwillingness to use effective contraceptive measures for the duration of the study and 4 months after discontinuation.

For male subjects: intent to procreate during the duration of the study or within 4 months after discontinuation or unwillingness to use effective measures of contraception. Oral contraceptives, Norplant®, Depo-Provera®, and barrier devices with spermicide are acceptable contraceptive methods; condoms used alone are not acceptable.

2. Received an islet transplant in a non-CIT research study.
3. Any medical condition that, in the opinion of the investigator, will interfere with safe participation in the trial.

## Glossary of Abbreviations

AE	Adverse Event
ATG	Anti-thymocyte Globulin
BG	Blood Glucose
CBC	Complete Blood Count
CFR	Code of Federal Regulations
cGCP	Current Good Clinical Practice
cGMP	Current Good Manufacturing Practices
CIT	Clinical Islet Transplantation Consortium
CRF	Case Report Form
CRO	Clinical Research Organization
CTCAE	Common Terminology Criteria for Adverse Events
DAIT	Division of Allergy, Immunology, and Transplantation
DCC	Data Coordinating Center
DCCT	Diabetes Control and Complications Trial
DSMB	Data Safety Monitoring Board
EC	Ethics Committee
FDA	Food and Drug Administration
GFR	Glomerular Filtration Rate
HbA1c	Glycosylated hemoglobin
HLA	Histocompatibility Antigen
HSV	Herpes Simplex Virus
ICH	International Conference on Harmonization
IND	Investigational New Drug
IRB	Institutional Review Board
ITN	Immune Tolerance Network
IV	Intravenous
MMTT	Mixed-Meal Tolerance Test
NIAID	National Institute of Allergy and Infectious Disease
NIDDK	National Institute of Diabetes and Digestive and Kidney Diseases
NIH	National Institutes of Health
PI	Principal Investigator
PTLD	Post-transplant Lymphoproliferative Disorder
SAE	Serious Adverse Event
SAP	Statistical Analysis Plan

SOP	Standard Operating Procedure
T1D	Type 1 Diabetes
TCAE	Terminology Criteria for Adverse Events

## Study Definitions

**Graft failure:** Islet allograft failure will be defined as absence of insulin production by transplanted islets, as evidenced by C-peptide < 0.3 ng/mL. This will be determined by (1) C-peptide <0.3 ng/mL on random testing, followed by (2) C-peptide <0.3 ng/mL at baseline, and at 60 and 90 minutes after MMTT. C-peptide levels obtained in the course of the MMTT will be run at the core lab in Seattle, WA; allow 72 hours for results. Participants with confirmed graft failure do not need to complete subsequent metabolic assessments.

**Islet allograft function:** A C-peptide  $\geq$  0.3 ng/mL at 0, 60, or 90 minutes after MMTT will be considered evidence of insulin production by transplanted islets. C-peptide levels obtained in the course of the MMTT will be run at the core lab in Seattle, WA; allow 72 hours for results.

**Parent studies:** CIT02, CIT03, CIT04, CIT05, CIT06, and CIT07.

**Severe hypoglycemia:** An event with one of the following symptoms: memory loss; confusion; uncontrollable behavior; irrational behavior; unusual difficulty in awakening; suspected seizure; seizure; loss of consciousness; or visual symptoms, in which the subject was unable to treat him/herself and which was associated with either a blood glucose level < 54 mg/dL [3.0 mmol/L] or prompt recovery after oral carbohydrate, IV glucose, or glucagon administration).

## 1. BACKGROUND AND RATIONALE

### 1.1 Background

The Clinical Islet Transplant Consortium opened in October 2004 under a research initiative (RFA-DK-04-005) sponsored by the National Institute of Diabetes and Digestive and Kidney Diseases (NIDDK) and the National Institute of Allergy and Infectious Diseases (NIAID). This consortium conducts seven trials in islet transplantation, six of which (CIT02, CIT03, CIT04, CIT05, CIT06, and CIT07) will be the source of study subjects in CIT08. Approximately 75 subjects are expected to be enrolled and followed in this trial.

### 1.2 CIT Parent Studies

The CIT studies aim to determine the safety and efficacy of islet transplantation with the goal of obtaining licensure in the U.S.

**CIT07 (phase III licensure study):** The primary objective is to demonstrate, in a multicenter, single-arm study, the safety and efficacy of islet transplantation for the treatment of T1D in subjects with hypoglycemia unawareness and a history of severe hypoglycemic episodes.

**CIT06 (phase III licensure study):** The primary objective is to demonstrate that islet transplantation in patients with established kidney transplants leads to improved metabolic control as measured by serial HbA1c levels and a reduced occurrence of hypoglycemic events.

**CIT02 (phase II pilot study):** The primary objective is to determine the proportion of subjects who are insulin independent at  $75 \pm 5$  days posttransplant after one islet transplant among subjects treated with lisofylline in addition to the standard islet transplant regimen used in the CIT-07 protocol.

**CIT03 (phase II pilot study):** The primary objective of this protocol is to assess the safety and efficacy of an immunosuppressive regimen consisting of ATG (1st transplant only), basiliximab (subsequent transplants only), etanercept, DSG, sirolimus, and low-dose tacrolimus on posttransplant islet function in subjects with T1D.

**CIT04 (phase II pilot study):** The primary objective of this protocol is to assess the safety and efficacy of an immunosuppressive medication consisting of a monoclonal antibody IL-2 receptor blocker (daclizumab or basiliximab), belatacept and mycophenolate mofetil in islet transplantation. The primary efficacy measure will be the proportion of insulin-independent subjects at day 75 ( $\pm 5$  days) following the first islet transplant.

**CIT05 (phase II pilot study):** The primary objective is to determine the proportion of subjects who are insulin independent at  $75 \pm 5$  days following the first islet transplant among subjects treated with an experimental islet transplant immunosuppression regimen which includes rituximab and excludes tacrolimus.

